This study will enroll up to 30 patients in order to evaluate 20 subjects. Infants will be screened for eligibility by the research team using routinely available clinical data from the electronic health record. Informed consent will be obtained from parents or guardians approached within the HUP ICN, PAH ICN, or the CHOP N/IICU during the eligibility window as described below. The diagram depicted in Figure 4 summarizes expected enrollment in consideration of our eligibility criteria and additional barriers to successful recruitment and study application. This estimate suggests a 10-month window of active enrollment will be required to meet our recruitment goals, making our one-year recruitment goal feasible. Aim 1 guides sample size considerations. Using a paired test of correlated means, a sample size of 20 evaluated infants will provide 80% power to detect an overall average percent change of 10% from baseline, assuming a 15% standard deviation of the difference and a two-sided alpha level of 0.05.

Key inclusion criteria

I1. 27-35 weeks corrected gestational age (CGA) by best obstetric estimate, determined by the clinical obstetric team during antepartum admission and chronologic age, measured from date of birth I2. Chronologic age greater than 24 hours, measured from time of birth. I3. On CPAP support between 4-8 cm H₂O for greater than 24 hours, as document on the bedside infant flow sheet. I4. Supplemental oxygen requirement, with a fraction of inspired oxygen (FiO₂) 0.25 for at least 2 consecutive hours, as documented on the bedside infant flow sheet. (Infants without an oxygenation requirement are unlikely to have significant V/Q mismatch. Further, FiO₂ titrations (see Procedures) are required to apply the non-invasive technique, resulting in limited applicability to infants with little or no supplemental oxygen requirement).

Key exclusion criteria

E1. Congenital anomalies, as determined by the clinical supervising physician. E2. Current or prior air leak syndrome, as determined by the clinical supervising physician.

Vulnerable Populations

Children Form

Pregnant women (if the study procedures may affect the condition of the pregnant woman or fetus) Form

Fetuses and/or Neonates Form

Prisoners Form

Other

None of the above populations are included in the research study

The following documents are currently attached to this item:

There are no documents attached for this item.

Populations vulnerable to undue influence or coercion

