
No active consideration of endotracheal intubation; as determined by the clinical Attending of record. 2. No hemodynamic instability, defined as a baseline heart rate less than 100 beats per minute (bpm) or greater than 180 bpm; or a mean arterial blood pressure of less than 30 millimeters of mercury (mm Hg). 3. No supplemental FiO₂ requirement greater than 0.45. 4. No capillary/arterial partial pressure of carbon dioxide greater than 65 mm Hg on last blood gas analysis, unless performed more than 6 hours prior. 5. No more than 6 apnea/bradycardia/desaturation events requiring tactile stimulation or more than 1 requiring positive pressure bag ventilation in the preceding 6 hours. Initiation of the study protocol will be deferred until these criteria are met. Figure 3 depicts the study protocol as applied in one hypothetical subject. Of note, the protocol will vary between subjects with respect to the direction and extent of CPAP level changes, as determined by the absence or presence of a response at each step-wise CPAP level change. This is described in detail below. Subjects will undergo the study interventions in their routine clinical environment. The clinically selected CPAP interface and pressure source will be maintained. A study pulse-oximeter, with low motion artifact and a short averaging time, will be placed on a post-ductal limb and used for SpO₂ measurements. V/Q will first be measured on two separate occasions 30 minutes apart at baseline CPAP, set by the clinical team. The repeat baseline measures will allow an estimate of the stability of V/Q as a function of time (further discussed in Confounding under Analysis Plan). To measure V/Q mismatch, gradual changes in delivered FiO₂, followed by SpO₂ measurement, will be applied to obtain three FiO₂/SpO₂ pairs, one each for SpO₂ values in the ranges of 85-87%, 89-91% and 93-95%. To obtain each SpO₂ range, FiO₂ will be titrated gradually until SpO₂ falls within the desired values. After 60 seconds of stabilization at the identified FiO₂ value, SpO₂ will be recorded every 30 seconds for 2 minutes if an adequate signal waveform is present, providing up to four SpO₂ values. These values will be averaged to calculate the SpO₂ value used for the FiO₂/SpO₂ pair, acknowledging the inherent instability of pulse-oximeter values over time in premature infants. A computer software program will immediately calculate V/Q from the identified FiO₂/SpO₂ pairs at the bedside. Next, CPAP will be increased by +1 cm H₂O. A period of 15 minutes will elapse to allow equilibration of lung volumes in response to the CPAP level change (24). V/Q calculations as described above will be repeated. A positive response will be defined as an improvement in V/Q at the new pressure level of 5% relative to the preceding CPAP level. Responders will undergo subsequent stepwise +1 cm H₂O increases up to +3 cm H₂O from baseline or 8 cm H₂O; whichever is less. Infants not responding to the initial +1 cm H₂O increase will return to baseline CPAP for 15 minutes and then be assessed at -1 cm H₂O from baseline. Infants responding at this lower CPAP level will undergo an additional decrease to -2 cm H₂O from baseline or 3 cm H₂O; whichever is greater. The allowed range of -2 to +3 cm H₂O reflects our institutional practice of typically setting a baseline CPAP level of 5 or 6 cm H₂O and a CPAP pressure range of 4 to 8 cm H₂O used in international trials. Best CPAP will be defined as the lowest (and last) CPAP level at which a positive response, as defined above, is measured. The baseline CPAP level will be defined as best for those infants not responding to either +1 or -1 cm H₂O CPAP level changes, with a corresponding V/Q improvement of zero. Upon completion of the study protocol, infants will be returned to their baseline CPAP level. The study protocol will typically require between 60 and 120 minutes. Throughout the study, a set of pre-defined stopping criteria will be monitored to ensure subject tolerance of the study procedures. These criteria are designed to be conservative safety measures and will result in study termination and provision of supportive care, as needed. Patient Safety Considerations: Extensive patient safety considerations minimizing the risks associated with implementation of this phase II design research protocol have been incorporated: 1. Many of the key eligibility (inclusions and exclusion) criteria reflect the deliberate selection of a premature infant population that is inherently less vulnerable and at lower risk of common morbidities of prematurity and less likely to suffer any adverse outcomes from implementation of the study procedures. a) I1. Corrected gestational age 27-35 weeks (GA): this selects a study population in which respiratory distress syndrome is common and CPAP is frequently used, while avoiding less mature infants with a CGA less than 27 weeks who are more prone to physiologic instability. We exclude this population in consideration of safety for this phase II study despite a high risk of CPAP failure and a potential for benefit from our long-term research goals of establishing methods to prevent CPAP failure. b) I2. Chronologic age of greater than 24 hours. This avoids study of infants during the first 24 hours of life when they may be more prone to physiologic instability. c) I3. On continuous CPAP support for greater than 24 hours. This prioritizes safety by restricting study to subjects demonstrating stability on CPAP therapy, in contrast to infants newly transitioned to CPAP without a period of demonstrated tolerance. d) I4. Supplemental oxygen requirement, with a fraction of inspired oxygen (FiO₂) 0.25 for at least 2 consecutive hours. This ensures that CPAP level changes are only performed in infants requiring supplemental oxygenation, suggesting V/Q mismatch and/or shunt from atelectasis. These subjects would plausibly benefit from carefully monitored changes in continuous distending airway pressure to counteract the pathophysiology resulting in the oxygen need. This criteria avoids CPAP

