Potential study risks are limited to the physiologic risks associated with changing CPAP and inspired supplemental oxygen. No direct psychological, social, economic, monetary, legal, or those risks that result from a loss of confidentiality is in any way anticipated. With respect to the physiologic risks associated with changing CPAP and FiO₂, several study design elements minimize the risk for harm in this phase II study. They are extensively detailed within "Patient Safety Considerations" in the "Procedures" section of this application. In summary, the eligibility criteria select a population in whom the study objectives are relevant, but who are less vulnerable to injury than extremely premature infants. The principal risks associated with the study procedures are those associated with over and under-distension of the lungs with CPAP level changes and the possibility of transient hypoxia and hyperoxia during FiO₂ changes. The former are minimized by the gradual step-wise changes in CPAP, ensuring that additional pressures are only tested when there is suggestion of improving physiology, and an evaluation restricted to a typical CPAP level range of 3 to 8 cm H₂O. Previous CPAP level trials in premature infants have studied levels as low as 0 cm H₂O and as high as 9 cm H₂O without reported concerns for harm (See Table 1). The latter will be limited by careful adherence to an accepted SpO₂ target range. Additional safety criteria to be verified immediately prior to application of the study interventions and comprehensive safeguards to protect against adverse events during the study interventions are described within "Procedures". Further, with respect to the physiologic risks imposed by the CPAP and FiO₂ changes, the likelihood and seriousness of these risks are minimal for the following reasons: 1. The CPAP levels evaluated reflect those used in routine clinical practice and levels assessed in international trials of CPAP therapy. 2. The CPAP level changes are transient and of short duration; the baseline clinical CPAP level is returned to at study termination. 3. The tested SpO₂ levels will be within 85-95%, the range consistent with acceptable target SpO₂ levels in international clinical practice. 4. A member of the research team will remain at the bedside throughout the study procedures, ensuring a greater degree of oxygen titration to target saturation levels than is often possible in routine clinical care. 5. All prior studies (Table 1) using CPAP level changes similar to and in times in excess of the range proposed in this study have either not reported concerns for adverse events or reported a lack of significant increase in adverse events as a result of study.

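### Each SpO₂ value behind the primary outcome rests on at most four spot readings, with undefined and unreplaced exclusions, taken by a team that knows the CPAP level and the preceding V/Q

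*Combined protocol and SAP*

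**What the plan says.** The Procedures section (Study Protocol) builds each V/Q estimate from three FiO₂/SpO₂ pairs, one in each of the ranges 85–87%, 89–91% and 93–95%. FiO₂ is titrated until SpO₂ is in range and 60 seconds are allowed for stabilization. Then: "SpO₂ will be recorded every 30 seconds for 2 minutes if an adequate signal waveform is present, providing up to four SpO₂ values". The next sentence reads "These values will be averaged to calculate the SpO₂ value used for the FiO₂/SpO₂ pair", and it acknowledges that oximeter values in these infants are unstable.

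The result is known at once: "A computer software program will immediately calculate V/Q from the identified FiO₂/SpO₂ pairs at the bedside". It is then judged against a threshold: "A positive response will be defined as an improvement in V/Q at the new pressure level of 5% relative to the preceding CPAP level". That judgement decides whether another CPAP step follows and which level is called best (Aim 2). It also decides which difference from the second baseline enters the primary analysis (Aim 1). Infants who respond neither at +1 nor at −1 cm H₂O are assigned an improvement of zero.

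The section on resources says members of the research team carry out the interventions, and Potential Study Risks adds "A member of the research team will remain at the bedside throughout the study procedures".

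The documents do not give a criterion for an adequate waveform, a minimum number of readings, a rule for replacing or logging rejected readings, a rule that the pairs are final before V/Q appears, or any blinding.

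**The concern.** An undefined exclusion judgement sits directly upstream of a 5% cut-off in an open, single-arm study. To apply the rule, the team must know the current pressure and the preceding V/Q. Because rejected readings are not replaced, a mean of one or two values counts the same as a mean of four.

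Two things follow. If low readings are lost more often at the new level than at the preceding one, the curve appears to move left and V/Q appears to improve. Separately, few spot values make each V/Q estimate noisier than the same window would allow, and noise alone can cross 5%.

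These errors do not cancel in the primary outcome. An infant whose noise points the wrong way at both +1 and −1 scores zero, while one whose noise points the right way scores a positive value.

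**Working it through.** **The plan's own figure.** Accrual states that "a sample size of 20 evaluated infants will provide 80% power to detect an overall average percent change of 10% from baseline". The other inputs given there are an SD of 15% for the paired difference and a two-sided test at the 5% level. For a paired t-test the noncentrality is (10/15)·√20 = 2.98 on 19 degrees of freedom, and the noncentral t gives 80.7% power. The stated 80% reproduces and is not in question here.

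**Inputs.** From the Procedures section: up to four readings per range, three ranges, 5% threshold. Not in the documents, hence assumed: reading SD *s* (SpO₂ points), local slope *b* (SpO₂ points per 1 point of % FiO₂) and right-shift *R* (% FiO₂). Readings are taken as independent and normal, the three pairs as equally weighted, and the curve shift as parallel.

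**1. Effect of losing the lowest of four.** Simulation gives an average rise of 0.343·*s* in the mean of that range. If this happens in *k* of three ranges at the new level only:

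apparent improvement = 0.343·*s*/*b* × (*k*/3) / *R*

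At *s* = 2.5, *b* = 1.5, *R* = 10:
- one range: 0.343 × 2.5/1.5 × (1/3)/10 = 1.9%
- all three: 0.343 × 2.5/1.5/10 = 5.7%

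Over a wide grid (*s* 1–3, *b* 1–4, *R* 5–30) the result is about 0.1–6.9% for one range and 0.3–20.6% for all three. One range alone reaches 5% only at the corner *R* = 5, *b* = 1, *s* = 3.

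If all four readings stayed within the 2-point range, the mean could rise by at most 2/4 = 0.5 point. At *R* = 10, *b* = 1 that caps the effect at 1.7% (one range) or 5.0% (all three). The plan does not require readings to stay in range after stabilization.

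**2. Noise with nothing dropped.** At *s* = 2, *b* = 2, *R* = 10:
- SD of a four-reading mean: 2/√4 = 1
- SD of the average over three ranges: 1/√3 = 0.577
- in % FiO₂: 0.577/2 = 0.289
- difference between two levels: 0.289 × √2 = 0.408, or 4.1% of *R*
- chance of exceeding 5%: P(Z > 5/4.08) = 11%; simulation using the measured preceding value as denominator gives 10%

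At *R* = 20 the SD of the difference halves to 2.0%, and the simulated chance is 0.6%.

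**3. Following the step rule with no true change.** The simulation allows up to three steps up, otherwise up to two down, with non-responders set to zero. Any dropping occurs only at levels after baseline.

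| Assumed *R*, *b*, *s* | Quantity | None dropped | Lowest dropped, one range | Lowest dropped, all three |
|---|---|---|---|---|
| 10, 2, 2 | false response, first step | 10% | 17% | 35% |
| 10, 2, 2 | mean recorded improvement | 1.2% | 1.9% | about 4% |
| 10, 1.5, 2.5 | mean recorded improvement | 3.1% | 4.5% | 8.0% |
| 20, 2, 2 | false response, first step | 0.6% | 1.4% | 5.5% |
| 20, 2, 2 | mean recorded improvement | about 0.1% | about 0.1% | 0.6% |

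The hypothesised improvement is 10%.

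**4. Precision available in the same window.** The comparison is four readings 30 seconds apart against 60 values 2 seconds apart over 120 seconds, with exponential autocorrelation. The variance of the mean (in units of *s*²) is:
- autocorrelation time 5 s: 0.251 against 0.081, a 68% reduction
- 10 s: 0.269 against 0.153, 43%
- 20 s: 0.348 against 0.278, 20%
- 30 s: 0.428 against 0.378, 12%

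**The case against.** The plan has real safeguards: an oximeter chosen for resistance to movement artefact, a stabilization minute, averaging, two baseline measurements, and a statement of high inter-rater reliability for the technique. These reduce noise. They do not define when a reading is rejected. The reliability statement carries no figure and is not shown to cover exclusions made with knowledge of the pressure. The repeat baseline is tested only for a mean change over time, so it cannot reveal selective loss at later levels.

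Four stronger readings are tempting, and the documents do not support them:

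- A reader might infer that SpO₂ is copied down by hand, or that waveform adequacy is purely an operator's opinion. The plan does not say how SpO₂ is captured or who or what judges the waveform. The phrase about recording by the research team concerns heart rate and blood pressure.
- A reader might infer that one dropped reading produces a 5% response. In the central case it moves V/Q by about 1.9%. Reaching 5.7% needs the lowest reading lost in all three ranges, at the new level only, and a very low reading may be a genuine artefact.
- A reader might infer that readings are chosen after the new V/Q is seen. In the described order the readings are averaged first and V/Q calculated afterwards, and nothing permits later editing. What is missing is an explicit rule against it.
- Deliberate manipulation is neither stated nor needed for the argument.

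It also stands that every driver of the size is assumed, and that the precision gain concerns SpO₂ error only, whose share of total V/Q error is unknown.

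**Conclusion.** The point holds as a weakness in how the primary measurement is taken, with a size the documents cannot fix. Few spot readings, an undefined and unreplaced exclusion, and a team aware of the pressure and the preceding result all feed a 5% rule whose false positives push Aim 1 in one direction.

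Under the scenarios in the table, the upward bias with no true effect runs from negligible (about 0.1% at right-shift 20 with nothing dropped) to most of the hypothesised 10% (8.0% at right-shift 10, slope 1.5, SD 2.5, lowest dropped in all three ranges). All of these rest on the assumed SD, slope and right-shift, independent readings and equal weighting of pairs. The spread of the differences between each infant's two baseline V/Q values would help show which scenario is closer, since it reflects measurement repeatability together with any change over 30 minutes. The stated power calculation is unaffected as arithmetic. The change is worth making because a better measurement is available from the same 2 minutes at small cost.

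**What to change.** In the V/Q measurement paragraph of Procedures:

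1. Average every SpO₂ value the study oximeter outputs over the existing 2-minute window, excluding only values that the device itself flags as low signal. Record how many were excluded.
2. If the device cannot supply this at the bedside, replace each rejected reading with the next 30-second reading, so that every mean has four values.
3. Enter and fix all three pairs before V/Q is displayed. No reading or pair is changed or repeated afterwards.

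**Cost.** The first item depends on the oximeter providing an output and a signal flag, which the documents do not confirm. The second may add a short time in a range, and the investigators would need to set a limit on it. No extra staff are needed. The CPAP steps and stopping criteria are untouched.

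Enrollment is under way, so infants already studied keep the old method. Each infant's baseline and later levels must use one method so that the paired difference stays internally consistent. The Analysis Plan should add a sensitivity summary of the primary outcome by measurement method.

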The objective of the proposed research is to evaluate a promising strategy for CPAP level selection: a physiologic approach minimizing V/Q mismatch and measured non-invasively at the infants bedside. We propose the following specific Aims and hypotheses in support of this objective: Aim 1 (primary): measure the responsiveness of V/Q mismatch to a strategy of individualized CPAP level selection. We hypothesize that V/Q mismatch will, on average, improve by 10% of baseline V/Q mismatch at the best identified CPAP level. Aim 2: describe the distribution of best CPAP levels as identified by our strategy. Best CPAP levels will be described as both absolute values and relative to baseline (+2 cm H₂O, -1 cm H₂O, etc.). For this exploratory aim, we hypothesize that a best CPAP will be identified above the baseline in greater than 50% but less than 80% of subjects. Demonstrating that most but not all infants benefit from higher pressures will highlight the importance of individualized CPAP level selection in premature infants.

Primary outcome variable(s)

Primary outcome measure: V/Q mismatch. This parameter will be calculated by computer software on the basis of the curvilinear characteristics generated by a best-fit curve connecting the FiO₂/SpO₂ pairs obtained during the study protocol. With lower V/Q and greater mismatch, the curve is progressively displaced to the right relative to a curve corresponding to an ideal reference lung (interrupted, left-most curve in Figure 2, see attached documents). The V/Q ratio is displayed on the software output after the FiO₂/SpO₂ pairs are input. Additionally, this parameter is also displayed as the degree of right-shift relative to the ideal reference lung (greater values indicate more mismatch), providing a positive continuous number with units of % FiO₂ as an alternative measure to the ratio value with greater ease of use. This will be measured twice at baseline without a change in CPAP level and then following each CPAP level change. The primary outcome measure is the responsiveness of V/Q mismatch to a strategy of individualized CPAP level selection, measured as the improvement in V/Q mismatch between the second baseline level and best identified CPAP level for each subject (see Figure 3 in attached documents.) For infants not responding to either +1 or -1 cm H₂O CPAP level changes, baseline CPAP will be defined as best, with zero assigned as the improvement in V/Q mismatch.

Secondary outcome variable(s)

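### Minor: the 8 cm H₂O limit is written only for later steps, so an eligible infant with a baseline of 8 would be tested at 9, outside the stated 3 to 8 range

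*Combined protocol and SAP*

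**What the plan says.** All references are to the combined protocol and SAP.

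- **Key inclusion criteria, I3.** Eligible infants are "On CPAP support between 4-8 cm" H₂O for more than 24 hours.
- **Procedures, Study Protocol, first step.** After the two baseline measurements, "Next, CPAP will be increased by +1 cm" H₂O. No condition is attached.
- **Procedures, later upward steps.** "Responders will undergo subsequent stepwise +1 cm H₂O increases up to +3 cm H₂O from baseline or 8 cm H₂O; whichever is less".
- **Procedures, downward steps.** "Infants not responding to the initial +1 cm H₂O increase will return to baseline CPAP for 15 minutes", and are then assessed at -1. Those who respond at -1 go on to -2 or to 3 cm H₂O, whichever is higher.
- **Primary outcome variable(s).** "For infants not responding to either +1 or -1 cm H₂O CPAP level changes, baseline CPAP will be defined as best, with zero assigned". The zero is that infant's primary outcome value. Procedures repeats this rule.
- **Potential Study Risks.** The limitation of tested levels to 3 to 8 cm H₂O is listed among the measures that reduce the risk of over- and under-distension. The same section notes that earlier studies went as high as 9, with no harm concerns reported.
- **Procedures, usual practice.** The institution is described as "typically setting a baseline CPAP level of 5 or 6 cm" H₂O.

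**The concern.** For a baseline of 8, the first-step rule and the stated safeguard cannot both be followed. Staff must either test at 9, against the risk description given to the IRB, or stop at 8 and depart from the written sequence.

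The second choice leaves a gap that reaches the primary outcome. An infant who never receives +1 has not failed to respond to it. So no written rule takes that infant to -1, and none sets baseline as best with zero improvement.

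The first choice also has a consequence beyond the step itself. If the infant responds, best CPAP becomes 9, a level outside the declared range. It would enter the Aim 2 distribution and be available to the clinical team, with whom study information is shared (Potential Study Benefits).

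**Working it through.** **The plan's own figure.** Accrual gives 20 evaluated infants for 80% power (change 10%, SD of the difference 15%, two-sided alpha 0.05). A paired t-test has noncentrality (10/15) × √20 = 2.98 on 19 degrees of freedom, giving power of 80.7% (78.5% at n = 19). The figure reproduces, and the present point does not depend on it.

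**Step rules.** Let b be the baseline, 4 to 8 (I3).

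- First upward level: b + 1
- Limit on later upward levels: min(b + 3, 8)
- First downward level: b - 1
- Lowest second downward level: max(b - 2, 3)

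| b | First up | Limit on later steps | First down | Second down | Outside 3 to 8? |
|---|---|---|---|---|---|
| 4 | 5 | 7 | 3 | 3 | No |
| 5 | 6 | 8 | 4 | 3 | No |
| 6 | 7 | 8 | 5 | 4 | No |
| 7 | 8 | 8 | 6 | 5 | No |
| 8 | 9 | 8 | 7 | 6 | Yes |

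**Size of the excess.** The first step passes 8 only when b + 1 > 8, that is b > 7. The excess is b + 1 - 8 = b - 7, at most 1 cm H₂O at b = 8. The lower limit of 3 is never passed. The tested range as written is therefore 3 to 9.

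**Duration of a completed first step.** Two rules apply: "A period of 15 minutes will elapse to allow equilibration of lung volumes", and for each of three FiO₂/SpO₂ pairs, "After 60 seconds of stabilization at the identified FiO₂ value, SpO₂ will be recorded every 30 seconds for 2 minutes". The minimum is 15 + 3 × (1 + 2) = 24 minutes, plus the time spent titrating FiO₂.

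**Is 8 eligible?** I3 does not say whether its endpoints are included, but the floor of 3 helps. With whole-number settings, b - 2 falls below 3 only at b = 4. If 4 were excluded, the floor would do nothing. That supports reading both endpoints as included.

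**Does the omission look deliberate?** An infant at 6 who responds at 7 and at 8 is stopped from going to 9 by the limit. An infant at 8 goes to 9 with no earlier response. Patient Safety Considerations treats making further changes conditional on response as a central protection, so the omission looks like a drafting slip.

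**The case against.** The strongest reply is that 8 was meant as the ceiling for every upward step. Potential Study Risks gives 3 to 8 as the tested range, and Procedures ties the allowed changes to the 4 to 8 used in international trials. Read together, no infant would be tested at 9. This is a plausible account of the intent, but it exchanges a conflict for a gap: the infant who skips +1 still has no written route to -1 and no written outcome value.

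Other points stand in part:

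- **Eligibility of 8** is an inference. It is the likelier reading, but I3 does not state it.
- **Practical effect is slight.** The case needs a baseline above 7. The step is 1 cm H₂O, with a research team member at the bedside and stopping criteria in force, and the attending physician may decline participation. The documents do not say how many infants had such a baseline.
- **The 24 minutes** applies only to a completed step; a stopping criterion would end it sooner.
- **A small trained team could handle one boundary case consistently.** That lessens the concern but does not supply the missing rule.
- **Other remedies exist**, such as limiting I3 to baselines of 7 or less. They are weighed under the fix.

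None of this removes the inconsistency. It supports grading the point as minor.

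**Conclusion.** The point holds and is minor. As written, an infant with a baseline of 8 is tested at 9, 1 cm H₂O above the range given as a safeguard. If staff stop at 8 instead, neither the next step nor the primary outcome value is defined for that infant.

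This rests on two readings: that I3 includes 8, and that the limit binds only the sentence containing it. Only the first is needed for the gap; testing at 9 needs both.

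The safety concern is small and the case is probably rare. Sample size, power and the planned tests do not change.

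**What to change.** Add to the Study Protocol part of Procedures:

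> The 8 cm H₂O limit also applies to the first step. An infant for whom +1 would exceed 8 skips it and is assessed at -1 from baseline, then at -2 if responding. If there is no response at -1, baseline is best, with an improvement of zero.

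Repeat the last sentence with the zero rule in Primary outcome variable(s).

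**Cost.** These infants lose the +1 measurement and cannot have a best CPAP above baseline in Aim 2. Some may be assigned zero in Aim 1 when they might have responded at 9. With 20 evaluated infants, each such case lowers the Aim 1 mean by 5/20 = 0.25 percentage points if the lost response was 5% (the response threshold), or 10/20 = 0.5 points if it was 10%.

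**Alternatives.** Limiting I3 to baselines of 7 or less leaves the step and zero rules untouched but narrows eligibility. Raising the stated range to 9 keeps the +1 measurement but loosens a safeguard, and it would sit oddly with stopping an infant at baseline 6 from reaching 9. The addition above keeps eligibility unchanged, holds every tested level within 3 to 8, and gives each baseline a defined path. Because accrual continues until 20 infants have undergone the intervention (Modification Summary), an affected infant could still enrol.
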